4.2 SUPPORTIVE CARE

4.2.1 *General Principles of Supportive Care*

Medications may be administered as clinically indicated, or at the discretion of the Principal Investigator, with the exception of other specific therapies for KS

4.2.2 Febrile Neutropenia

Subjects who develop febrile neutropenia will be hospitalized and treated with appropriate broad-spectrum intravenous antibiotics. See Section [3.3](#) for treatment modifications and guidelines for filgrastim use pertaining to neutropenia.

4.2.3 Anemia

If subject develops symptomatic anemia, or if the hemoglobin falls below 8.0 mg/dL transfusion may be considered. Appropriate evaluation for etiology of the anemia, including but not limited to pomalidomide, HIV and its therapy, should be initiated.

4.2.4 Thrombocytopenia

Thrombocytopenia should be treated conservatively. In the absence of bleeding or a planned invasive procedure, platelet transfusions should be given for a platelet count below 10,000/mm³. For subjects with risk factors for bleeding, including fever, platelet transfusion may be considered for platelet counts below 20,000/mm³. If invasive procedures are planned or the patient develops bleeding, platelet transfusions should be administered in accordance with standard of practice, usually maintaining a platelet count > 50,000/mm³.

4.2.5 Opportunistic Infections

Subjects who develop opportunistic infections, including but not limited to *pneumocystis jiroveci* pneumonia, mycobacterial diseases, cytomegalovirus (CMV), and fungal infections will be treated using standard regimens. All opportunistic infections will be discussed with the Principal Investigator. Consultation with the Infectious Disease Service is mandatory for subjects diagnosed with mycobacterium tuberculosis.

4.2.6 Nutritional Assessment and Psychological Support

- 4.2.6.1 HIV and KS may compromise nutritional status. Careful attention will be paid to nutritional status, and consultation with nutrition healthcare workers to optimize caloric intake will be undertaken as necessary.
- 4.2.6.2 The chronic, incurable and potentially life-threatening nature of this disease and the stigmatizing nature of visible lesions is a profound psychological stressor. All such subjects on the study will be informed of and encouraged to see a NIH Social Worker for evaluation and support.

5 BIOSPECIMEN COLLECTION

5.1 CORRELATIVE AND PHARMACOKINETIC STUDIES FOR RESEARCH.

Correlative studies to be performed during treatment with pomalidomide include assessment of changes in tumor blood flow by non-invasive imaging techniques([147](#), [148](#)); assessment of changes in systemic cytokines and angiogenic factors including IL-1 β , IL-2, IL-5, human IL-6, viral IL-6, IL-8, IL-10, IL-12, IFN- γ , TNF- α , VEGF-A, IP-10/CXCL-10 and RANTES; assessment of changes in HIV and KSHV viral loads (VL), including changes in HIV VL occurring below the conventional limit of detection; assessment of biochemical changes in KS tumor tissues (including the Notch ligands Dll1, Dll3, Dll4, Jag1 and Jag2; the Notch receptors Notch1, 2, 3 and 4; Notch intracellular domain (ICD); the Notch target genes Hey1 and Hey2; the transcription factors ZEB1, ZEB2, Slug and snail; EphrinB2 and EphB receptors; and markers of

NFkB activation [p65, p50IkBalpha and IKK1]); and preliminary assessment of changes in immunologic parameters, including monocyte activation, T-cell activation and subsets, and anti-KSHV specific T-cell immune responses. Correlative assays may be performed in batches.

5.1.1 Pharmacokinetic studies

Pharmacokinetic studies will be performed during the first course of therapy at the time of first dose (day one to two of cycle one), and be repeated at steady state (day 15 to 16 of cycle one).

5.1.1.1 Pharmacokinetic sample collection and analysis will be carried out in all enrolled subjects. For determination of pomalidomide pharmacokinetics, serial venous blood samples (6mL sodium heparin tube) will be obtained before and after drug administration on day 1 of cycle 1 (first administration) and day 15 of cycle 1 (steady state). The following time points for collection will be used: pre-dose, 1, 2, 3, 4, 6, 8, 24, according to the following table, in order to capture a fair estimate of the C_{max} and terminal elimination phase.

5.1.1.2 Pharmacokinetic Sample Schedule for Pomalidomide (times as close as feasible to those specified):

Cycle	Day	PK Sampling	Scheduled Time	Tube
1	1	Pomalidomide	Pre-dose	1
1	1	Pomalidomide	1 hour after dose	2
1	1	Pomalidomide	2 hours after dose	3
1	1	Pomalidomide	3 hours after dose	4
1	1	Pomalidomide	4 hours after dose	5
1	1	Pomalidomide	6 hours after dose	6
1	1	Pomalidomide	8 hours after dose	7
1	2	Pomalidomide	24 hours after dose	8
1	15	Pomalidomide	Pre-dose	9
1	15	Pomalidomide	1 hour after dose	10
1	15	Pomalidomide	2 hours after dose	11
1	15	Pomalidomide	3 hours after dose	12
1	15	Pomalidomide	4 hours after dose	13
1	15	Pomalidomide	6 hours after dose	14

Cycle	Day	PK Sampling	Scheduled Time	Tube
1	15	Pomalidomide	8 hours after dose	15
1	16	Pomalidomide	24 hours after dose	16

5.1.1.3 Handling of Pharmacokinetic Samples

- 5.1.1.3.1 The Blood Processing Core (BPC) ([name] Laboratory. 5A-09, [contact] or [contact]) will coordinate sample collection, processing and pharmacokinetic analysis. Research nurses will give the lab 24 hours advance notice on PK blood draws.
- 5.1.1.3.2 The date, planned time and exact draw time and cycle day of collection for each specimen will be recorded on a pharmacokinetic form containing the study number and unique patient identifier. The exact time of draw and cycle timepoint will be recorded by research or floor nurses on the blood tube label.
- 5.1.1.3.3 Research nurses will page [name] ([name] laboratory) immediately prior to blood draw. Blood will be drawn into green-top tubes to which 0.1% hydrochloric acid has been added. These will be supplied in capped tubes by the [name] laboratory to the clinical team prior to the patient starting treatment. After drawing, blood samples must be thoroughly mixed for drug stability and placed immediately on wet ice for transport to the [name] laboratory.
- 5.1.1.3.4 Samples will then be centrifuged within 30 minutes of collection, for 10 minutes at 2000g (4°C), and plasma supernatants will be transferred to individually labeled tubes, barcoded, anonymized, and stored at -80 °C until analysis. Patient data will be entered into a secure and encrypted LabSamples database maintained by the Clinical Pharmacology Program, Office of the Clinical Director.
- 5.1.1.3.5 An ultra high pressure liquid chromatography-tandem mass spectrometry analytical method will be used to quantify pomalidomide plasma concentrations.
- 5.1.1.3.6 Pharmacokinetic parameters calculated by noncompartmental analysis will be the maximum plasma concentration (C_{max}), the time at C_{max} (T_{max}), the C_{max} at steady-state ($C_{max\ ss}$), $T_{max\ ss}$, apparent clearance (CL/F), and the apparent volume of distribution (Vss/F), the area under the plasma concentration time curve on day 1 extrapolated to infinity ($AUC_{0-\infty}$) and at steady state (AUC_{0-24}), terminal elimination half-life ($T_{1/2}$). The study will include exploratory population pharmacokinetic correlative analysis of drug-interaction effects on pomalidomide plasma exposure for subjects on antiretroviral medications.

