1 INTRODUCTION

1.1 STUDY OBJECTIVES

1.1.1 Primary Objective:

- Assess the safety, tolerability and pharmacokinetics of pomalidomide at an oral dose regimen of 5mg once daily for 21 days of a 28 day cycle in subjects with Kaposi sarcoma, whether HIV associated or not, or in the case that the initial dosing schedule of pomalidomide is not tolerated, assess the safety, tolerability and pharmacokinetics of pomalidomide at 3mg daily for 21 days of a 28 day cycle.

1.1.2 Secondary Objectives:

- Explore in a preliminary manner the antitumor effect of pomalidomide at whichever of the dosing schedules described above is determined to be tolerable
- Assess the variation in pomalidomide pharmacokinetics in relation to common antiretroviral agents, especially potentially nephrotoxic agents such as tenofovir
- Assess changes in quality of life in subjects receiving pomalidomide
- Explore in a preliminary manner the safety, tolerability and antitumor effect of a second course of pomalidomide in patients who manifest KS requiring therapy after deriving clinical benefit from initial treatment with pomalidomide.

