1.2.3.3 Pharmacology

The pharmacokinetics of pomalidomide were characterized in healthy male subjects at doses from 1 to 50mg (single administration)([108](#)). Following oral dosing, there was moderately rapid absorption with a C_{max} that was less than dose proportional occurring at a median t_{max} of 2.5 to 6 hours post dose. After reaching C_{max} , plasma concentrations of pomalidomide declined in an apparent biphasic manner. The systemic exposure of pomalidomide, as determined from the area under the plasma concentration time curve (AUC_{0-tz} and $AUC_{0-\infty}$) increased in an approximately dose proportional manner. The $T_{1/2}$ ranged from 8.2 to 10.8 hours, with no apparent dose-related trend. Excretion was urinary, predominantly as metabolites. These characteristics were very similar to those seen in a separate phase 1b study in subjects with multiple myeloma^{[119](#)}.

Pomalidomide did not inhibit CYP 1A2, 2B6, 2C8, 2C19, 2D6, 2E1 or 3A4/5 activity in human liver microsomes *in vitro* ($IC_{50}>30\text{ }\mu\text{M}$; <10% inhibition at 30 μM)([108](#)). Treatment of cultured hepatocytes with up to 3 μM pomalidomide twice daily for three consecutive days caused no changes in any of the CYP enzyme activities examined (1A2, 2B6, 2C9, 2C19 and 3A4/5). Hence pomalidomide is not likely to cause drug/drug interactions due to enzyme inhibition or induction when co-administered with CYP substrates.

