14 PHARMACEUTICAL INFORMATION

14.1 POMALIDOMIDE

[figure not shown]
Description

Pomalidomide, 4-amino-2-(2,6-dioxo-3-piperidyl)isoindoline-1'-one)-1,3-dione, belongs to the IMiDs class of compounds. The Chemical Abstract Service (CAS) registry number for CC-4047

Abbreviated Title: Pomalidomide in Kaposi sarcoma

Version Date: 11/19/2021

is 19171-19-8. The chemical structure of the active pharmaceutical ingredient (API) is as follows:

Pomalidomide has an asymmetric carbon atom and can therefore exist as the optically active forms S (-) and R (+). Pomalidomide is being developed as a racemate.

Mechanism of Action

Pomalidomide is a novel member of a class of pharmaceutical compounds known as immunomodulatory drugs (IMiDs). It shares a number of the beneficial pharmacologic properties of thalidomide and lenalidomide, but it is a more potent anti-proliferative immunomodulating agent than either drug. The pharmacodynamic properties of pomalidomide are of potential therapeutic benefit in the treatment of several human tumors.

Supply

Celgene Corporation will supply POMALYST® (pomalidomide) through Celgene's Pomalidomide Risk Evaluation and Mitigation Strategy (POMALYST REMS™).

Dosage Form

Pomalidomide will be supplied as 1.0 mg, 2.0 mg, 3.0 mg and 4.0 mg capsules for oral administration.

Packaging

Pomalidomide will be shipped to the pharmacy at the study site in individual bottles. Bottles will contain a sufficient number of capsules to last for one cycle of dosing. Study drug must be dispensed in the original packaging with the label clearly visible.

Labeling

Pomalidomide investigational supplies are dispensed to the patients in individual bottles of capsules. Each bottle will identify the contents as study medication. In addition, the label will bear Celgene's name, quantity contained and the standard caution statement as follows: Caution: New drug - Limited by Federal law to investigational use. Pomalidomide should not be handled by FCBP unless wearing gloves.

The study drug label must be clearly visible. Additional labels must not cover the Celgene label.

Receipt of Study Drug

The Investigator or designee is responsible for taking an inventory of each shipment of study drug received, and comparing it with the accompanying study drug accountability form. The Investigator will verify the accuracy of the information on the form, sign and date it, retain a copy in the study file, and return a copy to Celgene or its representative.

Storage

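### Section 5.1.1.3.6 lists Vss/F as a noncompartmental parameter although dosing is oral only; it should list Vz/F, with the formula and study day stated

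*Combined protocol and SAP*

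**What the plan says.** Section 5.1.1.3.6 opens its parameter list with "Pharmacokinetic parameters calculated by noncompartmental analysis will be the maximum plasma concentration" and goes on to include "apparent clearance (CL/F" and "and the apparent volume of distribution (Vss/F" (each bracket closes straight after the F). The list also contains Tmax, the steady-state Cmax and Tmax, AUC to infinity on day 1, AUC over 24 h at steady state, and terminal half-life. It gives no formula for the volume, does not mention residence time or absorption time, and does not say which study day supplies CL/F or the volume. Vz/F is not listed.

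Dosing is oral throughout. The primary objective (section 1.1.1) specifies an "oral dose regimen of 5mg once daily for 21 days of a 28 day cycle", with a lower oral dose as the fallback, and section 14.1 describes the supply as "capsules for oral administration". No intravenous dose or formulation is described.

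Sampling is the same on days 1 and 15 of cycle 1. Section 5.1.1.1 states: "The following time points for collection will be used: pre-dose, 1, 2, 3, 4, 6, 8, 24". Section 1.2.3.3 reports, for single doses of 1 to 50 mg in healthy men, a median Tmax "of 2.5 to 6 hours post dose", a half-life that "ranged from 8.2 to 10.8 hours, with no apparent dose-related trend", and a biphasic decline after the peak.

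**The concern.** Vss is a specific quantity. In noncompartmental analysis it is clearance multiplied by the mean residence time of drug already in the body. After an oral dose, the residence time obtained from the concentration curve also counts the time spent being absorbed. Noncompartmental analysis of oral data alone cannot separate the two, so a Vss/F computed in the usual way is too large. Dividing by F allows for unknown bioavailability but does not remove absorption time. The bias comes from the definition, so enrolling more subjects does not shrink it.

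At stake is one reported parameter. Part of its value would reflect how fast the capsule is absorbed, and someone comparing it with a Vss from another source would not be comparing like with like.

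**Working it through.** The protocol states no value for the volume, so there is no figure of its own to reproduce. The check has four parts.

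**1. The identity.** Write MRT for disposition residence time and MAT for mean absorption time.

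- True value: Vss = CL × MRT.
- After an oral dose: AUMC/AUC = MRT + MAT.
- Uncorrected oral result: (CL/F) × (MRT + MAT).
- Ratio to the true Vss/F: 1 + MAT/MRT.

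MAT is above zero, so the ratio exceeds 1 whatever the number of compartments.

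**2. An illustrative size.** Inputs from section 1.2.3.3 are half-life 8.2 to 10.8 h and Tmax 2.5 to 6 h; the intermediate values 9.5 h and 4 h are added. Assume one compartment with first-order absorption:

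- k = ln 2 / half-life, and MRT = 1/k.
- ka solves Tmax = ln(ka/k)/(ka − k), and MAT = 1/ka.

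Example: half-life 8.2 h gives k = 0.693/8.2 = 0.0845 per h and MRT = 11.83 h. With Tmax 6 h, ka = 0.290 per h and MAT = 3.45 h, so the ratio is 1 + 3.45/11.83 = 1.292.

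**3. The protocol's sampling times.** Noncompartmental analysis (linear up, log down; λz from the 6, 8 and 24 h samples) was run on error-free concentrations from the same model at 0, 1, 2, 3, 4, 6, 8 and 24 h. The last two columns give the result relative to the true V/F.

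| Half-life (h) | Tmax (h) | MAT (h) | MRT (h) | 1 + MAT/MRT | Vss/F on schedule | Vz/F on schedule |
|---|---|---|---|---|---|---|
| 8.2 | 2.5 | 0.90 | 11.83 | 1.076 | 1.094 | 1.009 |
| 8.2 | 4 | 1.80 | 11.83 | 1.152 | 1.178 | 1.037 |
| 8.2 | 6 | 3.45 | 11.83 | 1.292 | 1.407 | 1.225 |
| 9.5 | 2.5 | 0.84 | 13.71 | 1.061 | 1.078 | 1.008 |
| 9.5 | 4 | 1.67 | 13.71 | 1.122 | 1.144 | 1.028 |
| 9.5 | 6 | 3.14 | 13.71 | 1.229 | 1.328 | 1.178 |
| 10.8 | 2.5 | 0.80 | 15.58 | 1.051 | 1.066 | 1.007 |
| 10.8 | 4 | 1.57 | 15.58 | 1.101 | 1.119 | 1.023 |
| 10.8 | 6 | 2.91 | 15.58 | 1.187 | 1.273 | 1.146 |

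In theory the overstatement of Vss/F is 5% to 29%; on the sampling schedule it is 7% to 41%. Vz/F = (CL/F)/λz has no MAT term and is exact in theory under this model. On the schedule it is 1% to 23% high. That excess comes from the terminal slope: nothing is sampled between 8 and 24 h, and with a late peak the 6 h sample is not yet on the terminal decline.

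**4. A two-compartment illustration,** because the reported decline is biphasic. The rate constants are assumed: k12 and k21 of 0.1 and 0.2, 0.3 and 0.3, or 0.05 and 0.2 per h, with k10 set to reproduce half-lives of 8.2 and 10.8 h. True Vz is then 1.09 to 1.24 times true Vss. With MAT of 0.75 to 3 h, the uncorrected oral Vss/F is 1.05 to 1.32 times the true value. Take k12 = 0.1, k21 = 0.2, half-life 8.2 h and central volume 1: Vss = 1.50, Vz = 1.87, and the uncorrected oral value at MAT 3 h is 1.50 + 0.158 × 3 = 1.97. At MAT 3 h it exceeds Vz in all six settings, which a true Vss cannot do.

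**The case against.** The strongest objection is that the formula is inferred. The protocol never writes CL/F times residence time. The same sentence uses an ss suffix for day-15 Cmax and Tmax and describes Vss/F only as an apparent volume of distribution. It could mean (CL/F)/λz taken at the steady-state visit; half-life is in the list, so λz is available. On that reading absorption time does not enter and only notation is at fault. This stands as a possible reading, but the line would still need changing: Vss/F is the standard symbol for a different quantity, and with a biphasic decline the two volumes differ.

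A second objection is that the size depends on a model, which is right. The half-life and Tmax are ranges across single doses in healthy men, the model has one compartment although the decline is described as biphasic, and the documents do not say that Tmax 6 h and half-life 8.2 h occurred together. At Tmax 2.5 h the theoretical figure is only 5% to 8%. The direction needs none of these assumptions.

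A third objection is that Vz/F has faults of its own. It does: it is larger than the true Vss/F when decline is biphasic, it moves with elimination even if distribution is unchanged, and on this schedule it may be 15% to 23% high when Tmax is 6 h.

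Two stronger readings are tempting. A reader might infer that comparisons of volume between antiretroviral groups would be distorted. No such comparison is planned: section 5.1.1.3.6 directs the drug-interaction analysis at plasma exposure, the secondary objective in section 1.1.2 speaks of pharmacokinetic variation in general, and the rationale in section 1.2.4.2 is renal excretion. A reader might also infer that the population analysis will supply an absorption-free volume. The protocol describes it as exploratory and names neither a structural model nor a volume output.

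**Conclusion.** The point holds as a minor one. As written, the plan names a volume that noncompartmental analysis of oral data cannot deliver without absorption-time bias; if another volume was intended, it is mislabelled. The upward direction rests only on the usual calculation, CL/F times observed residence time. The 5% to 29% is an illustration under a one-compartment model with first-order absorption and healthy-volunteer inputs, and 29% arises only at the extreme pairing. It is not an estimate of the error in this trial.

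Because pharmacokinetics is in the primary objective, a reader might infer that a primary result is compromised. The documents do not support that. Cmax, Tmax, AUC, CL/F and half-life do not carry this absorption-time bias. Dose selection in sections 3.1.3 and 3.1.5 rests on dose-limiting toxicity, and the analyses in section 10.4 make no use of volume.

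**What to change.** In section 5.1.1.3.6:

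- Replace Vss/F with Vz/F, and write the formula: Vz/F = (CL/F)/λz, with λz = ln 2 / terminal half-life.
- State which study day it comes from and which AUC defines CL/F on that day.
- State which samples determine λz.
- Report Vz/F as descriptive. Note that it is not Vss/F when decline is biphasic, that it varies with elimination, and that the absence of samples between 8 and 24 h may leave it somewhat high (about 1% to 23% under the model above).

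The cost is a few lines of text and a recalculation from the same concentrations. No new samples are needed, and no other parameter, dose decision or response analysis changes. What is given up is a steady-state volume, which noncompartmental analysis of these oral data could not supply free of absorption time.

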5.1.2 Correlative Studies

5.1.2.1 Sample Collection

5.1.2.1.1 Correlative Cytokine, Angiogenesis and Virologic Studies

Evaluations will occur on day 1 of each cycle as well as on day 29 of the final cycle. There will also be an additional pre-therapy collection for single copy HIV VL.

5.1.2.1.1.1 KSHV viral load in peripheral blood mononuclear cells

- One yellow top tube (send to [name] laboratory)

5.1.2.1.1.2 KSHV viral load in saliva

- One blue top conical polypropylene tube (no additive) of saliva obtained with Scope® mouthwash (BD Falcon® Ref 353070) (send to [name] laboratory).

5.1.2.1.1.3 viral IL-6, human IL-6, human IL-10, IL-1 β , IL-5 IL-8, IL-12, IFN- γ , TNF- α , RANTES and IP-10/CXCL-10

- Two red top tubes (send to Leidos Biomedical Research Inc., Frederick)

5.1.2.1.1.4 Measurement of VEGF, FGF-2, Dll4/Notch and Ephrinb2/Ephb2

- Three sodium heparin green top tubes (send for storage to Leidos Biomedical Research Inc. Frederick)

5.1.2.1.1.5 Single copy HIV VL (only in patients with HIV infection)

- One 6mL lavender top (EDTA) tubes for measurement of single copy HIV VL. Send to Leidos Biomedical Research Inc., Frederick to be frozen at -40°C. These samples will be transferred to the [name] laboratory when ready for batched testing. Samples will be run only in patients whose HIV VL by conventional techniques is approaching or below the limit of detection.

5.1.2.1.1.6 Two yellow top tubes (send for storage to Leidos Biomedical Research Inc., Frederick).

5.1.2.1.2 Immune Activation and KSHV Immune Response Assays

Studies will be performed on one occasion pre-therapy (to be after screening and enrollment and at least 2 days before commencement of therapy and repeated 28 days (\pm 7 days) after completion of the final cycle. Monocyte and T-cell Activation and Subset assays *only* will also be repeated day 1 of cycle 4. If a fresh monocyte sample is planned and the [name] laboratory is unable to receive the fresh monocyte sample on the day of a planned draw (for example due to staff illness, equipment failures, or other exigencies) the fresh monocyte sample may be drawn on the next available cycle or run from frozen specimens without constituting a protocol deviation; for the pre-therapy draw samples may be drawn any day prior to drug administration up to and including cycle 1 day 1.

If immune activation studies and KSHV immune response assays have been performed on a subject as part of the HAMB Tissue Procurement study (01-C-0038) within 14 days of enrolment on 12-C-0047, then at the discretion of the Principal Investigator or Lead Associate Investigator the samples drawn under 01-C-0038 may be used for the pomalidomide pre-therapy baseline and this draw does not need to be repeated pre-therapy. In these cases, the investigator will confirm that the patient gave consent for future use of specimens when the consent for 01-C-0138 was signed.

5.1.2.1.2.1 KSHV Serology, KSHV miRNA Typing and KSHV-specific T-cell Responses

- Performed in the laboratory of [name], NCI-Frederick.
- Serology and miRNA Typing will be performed at the pre-therapy draw only.
- Samples for KSHV-specific T-cell Responses will be stored and performed in batches with paired samples from individual subjects assayed together for consistency.

- Send 34mL blood in four yellow top (ACD) tubes to Leidos Biomedical Research Inc., Frederick for storage prior to transfer to [name] laboratory.

5.1.2.1.2.2 Monocyte and T-cell Activation and Subset Assays

- Performed in the laboratory of [name], NIAID.
- As of amendment E, fresh monocyte studies from EDTA samples will not be performed. Monocyte studies will be performed from frozen sodium heparin samples.
- T-cell studies will be stored and performed in batches with paired samples from individual subjects assayed together for consistency: send 40mL blood in green top (sodium heparin) tubes to Leidos Biomedical Research Inc., Frederick for storage.

